## 2.2.2 Secondary Objectives

These are given below. Their purpose is to provide timely information on:

Version 40 20/11/2014 REC Ref 12/SC/0592

(i) Prescriber and cohort accrual and the type of prescriber responsible for, and the setting of initiation of treatment with either rivaroxaban or alternative anticoagulant therapy.

(ii) Prevalence of non-clinical reasons for prescribing, prognostic health factors and clinical risk factors for haemorrhage as reported in medical charts for patients undergoing anticoagulation with either rivaroxaban or alternative anticoagulant therapy in the secondary care hospital setting and the treatment programme they received to advance the understanding of the patient population prescribed rivaroxaban in actual clinical practice in the secondary care hospital setting

(iii) Changes of health profile of patients, assessment of adherence, plus any alterations of the treatment programme during the 12 week observation period, as recorded in medical charts.(iv) To quantify the risk of:

(a) (separately) haemorrhage within gastrointestinal and urogenital organ sites (which meets the criteria for a major bleed) and all intracranial sites for contextual anticoagulant therapy cohort

(b) all major bleeding specified in primary objective for both rivaroxaban and contextual anticoagulant therapy cohort (as composite)

(c) (separately) haemorrhage (major bleeding according to Table 2) within critical organ sites other than specified in primary objective for both rivaroxaban and contextual anticoagulant therapy cohort

(d) all major and clinically relevant non-major bleeds (as a composite outcome)

(e) thromboembolic complications (incident and recurrent)

(f) other†† events including special outcomes of interest (severe hepatic failure and abnormal LFTs above 3x ULN) as recorded in medical charts during the 12 week observation period and, if number of reports are sufficient, in patient subgroups of special interest, including:

- reported indications
- elderly (>= 65 years)‡‡, other contraindicated or special groups (e.g. pregnant and breastfeeding women, patients with concurrent significant renal or hepatic impairment; patients with known VTE and/or haemorrhagic risk factors e.g. congenital or acquired bleeding disorders, uncontrolled severe arterial

<sup>†† Other than major and clinically relevant non major bleeding outcomes, or thromboembolic complications (recurrent or incident)

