Since this is a new user inception or incidence rivaroxaban cohort that is being identified, this study avoids the introduction of a number of biases associated with existing users (including incidence/prevalence bias, survivorship bias, and follow-up bias) which may impact on the measure of frequency of primary objective. Data will also be available for the internal contextual cohort which will have been collected during the same calendar period, for similar indications using the same data collection methods, and all subject to the same protocol. This minimises effect of bias from non-random measurement error. However, whilst users of anticoagulant therapy appear to provide a 'logical' contextual cohort that may be similar with regard to some clinical risk factors, they may also differ with respect to other important confounding factors such as disease severity. The key purpose of this contextual cohort is to explore the variation in the distribution and determinants of prognostic and clinical risk factors. It is not to compare risk of primary outcome between the two groups.

The first part of the second phase of the study will involve participating specialist HCPs capturing (in anonymised format using patient unique identifier) brief summary data (e.g. sex, age, indication, bleeding/stroke risk score and non-clinical reasons for prescribing) as recorded in the medical charts for **all** individuals invited to participate (including those who declined) for whom the clinical decision to prescribe rivaroxaban or alternative anticoagulant therapy was made under conditions of real life practice. These data will help examine the representativeness of the study population.

Cohort recruitment will be examined regularly to monitor the number of evaluable patients included, so as to ensure that the desired ratio of 1:1 rivaroxaban: contextual cohort patients with the relevant indications is achieved in the final overall study cohort for secondary objective analysis.

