# 4.7.2 To estimate the cumulative incidence of the important identified risk of haemorrhage for rivaroxaban.

The following relates to Section 2.2.1 primary objective (i) for rivaroxaban only and relates to haemorrhage within gastrointestinal and urogenital organ sites (which meets the criteria for a major bleed) and all intracranial sites (as defined in Table 2)..

For the three organ sites specified in the primary outcome, each of the individual components of the major bleeding criteria (a fall in haemoglobin of 2 g/dL or more, or a transfusion of 2 or more units of packed red blood cells or whole blood, or a fatal outcome - as per table 2) will be summarised. Where an individual has one or more criterion for an individual organ site of interest, this will also be summarised – in such individuals the first report will be regarded as the incident event. The cumulative incidence (risk) of the primary outcomes reported during treatment within the 12 week observation period will be explored by estimating the cumulative incidence of incident reports (plus 95% CI) and cumulative hazard rates (plus 95%CI) of incident events over time. For purposes of this analysis the denominator (personperiod at risk) is defined as the 12 week observation period (i.e., the time from the date the first prescription was issued for rivaroxaban (treatment index date) until the date of stopping (+ 2 days) or at 12 weeks if patient did not stop, whichever occurs first). The numerator will comprise of reports of incident major bleeding events during that 12 week observation period. These which have been adjudicated by expert review (using all available information from SCEM questionnaires, follow-up and any additional documentation). Where such information reveals that the event was misreported, that patient will excluded as a case from the analysis, but contribute person-time exposed.

The cumulative incidence will be calculated according to the formula:

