# Total number of new cases during 12 week observation period x 100 Population initially at risk

If the observed cumulative incidence from the SCEM study falls within the range expected as set by the precision limits of cumulative incidence from clinical trial data, then the null hypothesis (of no difference) will not be rejected. Cumulative hazard rate methods account for truncation of exposure time and censoring; for these analyses the exposure time would be censored at the time of the first event. Kaplan-Meier plots will be presented to describe timeto event as well as smoothed hazard plots to describe how the baseline risk of an event changes over time. Estimates of the hazard function will also be modelled to determine whether the baseline hazard (risk) of the event increases or decreases with time. A constant hazard over time may be consistent with a background (not caused by the drug) event rate, whereas a non-constant hazard over time may be an indicator of a drug-event relationship. The null hypothesis that the hazard rate of the selected event in patients prescribed rivaroxaban will be constant during the 12 week period following the start of treatment will be tested by fitting a parametric time to event model (e.g. Weibull). Such models have a shape parameter that indicates whether the hazard is significantly increasing or decreasing over time. At least five reports of an event are deemed necessary for modelling purposes.\*\*\*\*\*\*

Several sensitivity analyses will be performed: In one, observation start date will be imputed to be the same as the diagnosis date (i.e the index date will be shifted backwards in time) for those patients for whom a lag period between diagnosis and receiving rivaroxaban treatment was reported. The application of time-varying covariates methodology will enable examination of the impact of any transition from other treatments given as part of initial standard care on the results. In addition, since the primary analysis will be run only to include confirmed cases of incident major bleeding, it will be necessary to explore the reasons for exclusion of incomplete cases and examine their impact on the estimated measure of frequency.

Where possible, data will be stratified according to relevant strong risk factors (e.g. gender, age ( $\leq 60, 60-74, \geq 75$  years), indication and past history of haemorrhage or VTE) and stratum-specific incidence rates examined.

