The following relates to Section 2.2.2 secondary objective (iii) Status of indication-related characteristics (alteration of diagnosis, stroke (CHADS2/ CHA2DS2-VASc) and bleeding risk score (HAS BLED) if available) will be summarised, plus pattern of anticoagulant treatment adherence at the end of the 12 week observation period (as estimated from Medication Possession Ratio††††††) will be summarised. The frequency and reasons for attendance to clinics for review and management of anticoagulation and/or acute hospitalisations (including hospital referrals) will also be summarised, where reported. Alterations in treatment programme (change in dose, other drugs) will be described, as will any reason(s) for stopping treatment (including switching) and transition plans to other anticoagulants.

Changes in these indication-related characteristics and treatment details will be examined by comparing values at index and at 12 weeks post index date. Exploratory analysis may include data mining and descriptive measures for describing alterations in treatment programme.

The number of pregnancies, trimester of first exposure and details of births, terminations and miscarriages will be presented. The number of deaths (as recorded in medical charts) in the total cohort for each month of exposure will be calculated. Causes of death will also be described by system-organ class.

Sensitivity analyses will examine any under-reporting using data provided from the patients GP.

Where no. days held will be calculated from information derived from 12 week questionnaire on number of prescriptions and average treatment length of prescriptions (usually given in 7, 14,28,56 day repeats); no. days supply expected will assume chronic use from start to end of study observation or treatment stop date (if stopped)

4.7.5 To quantify the incidence risk and rate of events reported in the 12 week observation period in both the rivaroxaban and contextual cohort and in patient subgroups of special interest.

The following relates to Section 2.2.2 secondary objectives (i) and (iv) regarding a) major bleeding outcomes as specified in the primary objective for the contextual cohort, b) other major or non-major clinically relevant bleeding outcomes not specified in the primary objectives, c) thromboembolism (recurrent and incident) and d) any other events reported in the 12 week observation period.

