For major bleeding events not specified in the primary outcome, each of the individual components of the major bleeding criteria ( a fall in haemoglobin of 2 g/dL or more, or a transfusion of 2 or more units of packed red blood cells or whole blood, or a fatal outcome - as per table 2) will be summarised. Where an individual has one or more criterion for an individual organ site of interest, this will also be summarised – in such individuals the first report will be regarded as the incident event.

For clinically relevant non-major bleeding events, each of the individual associated components (as per table 2 such as requiring medical intervention, unscheduled contact (visit or telephone call) with a physician, (temporary) cessation of study drug treatment, or associated with discomfort for the subject such as pain or impairment of activities of daily life) will be summarised. Where an individual has one or more criterion for a clinically relevant non-major bleeding event, this will also be summarised – in such individuals the first event report will be regarded as the incident event.

Analysis of event data for purposes of signal detection includes exploring overall risk and rate for the observation period and time to onset profiles. The methodology provides a numerator (the number of reports of an event) and a denominator (person-time at risk), both collected within a known time frame. This allows for the calculation of crude risks (percent of total valid cohort exposed) and rates (Incidence Densities-ID; person-time incidence rates) for each event separately. Each event may be reported in response to a closed question (for example information on each individual major and/or clinically relevant non-major bleeding risk component), or as free text in response to open questions on the data collection forms. Such analyses will be performed using 'Higher-level' event terms from the MedDRA dictionary where possible. The risk profile of the overall cohorts and sub-group of interest

(based on index date characteristics, including whether anticoagulant naïve, rivaroxaban naïve or past (other anticoagulant user) will be described by presenting summary tabulations (by rank) of counts and incidence risk of reported events, and crude event rates (IDs).

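### Expert adjudication and removal of misreported GI, urogenital and intracranial bleeds is specified for rivaroxaban only; no such rule is stated for the same bleeds in the contextual cohort

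*Supplement*

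**What the plan says.** **Rivaroxaban.** Section 4.7.2 sets its own scope: "The following relates to Section 2.2.1 primary objective (i) for rivaroxaban only". Its numerator is reports of incident major bleeding, with the qualification "These which have been adjudicated by expert review (using all available information from SCEM questionnaires, follow-up and any additional documentation". It then gives a removal rule: "Where such information reveals that the event was misreported, that patient will excluded as a case from the analysis, but contribute person-time exposed". Later in the same section the restriction is restated as the reason for a sensitivity analysis: "since the primary analysis will be run only to include confirmed cases of incident major bleeding".

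**Contextual cohort.** Secondary objective (iv)(a) in Section 2.2.2 asks for the risk of the same outcomes: GI and urogenital bleeds meeting the major-bleed criteria, and "all intracranial sites for contextual anticoagulant therapy cohort". Section 4.7.5 takes these on as its item a), "major bleeding outcomes as specified in the primary objective for the contextual cohort". Its description of the method reads "The methodology provides a numerator (the number of reports of an event) and a denominator (person-time at risk". The first report in a patient is the incident event. No expert review, confirmation step or case-removal rule for these bleeds appears in that section.

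**Both cohorts together.** Objective (iv)(b) asks for a composite of the primary-site bleeds in both cohorts. Section 4.7.6 would explore the effect of oral anticoagulant, among other predictors, on haemorrhage and report odds ratios with 95% intervals, but only if there are enough cases. Section 4.3.2 says the contextual data come from the same calendar period, by the same collection methods and under the same protocol, and adds: "This minimises effect of bias from non-random measurement error". That section and the Executive Summary both state that comparing primary-outcome risk between the cohorts is not the purpose.

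**The concern.** Adjudication of this kind can only take cases away. If one cohort's count has had false reports removed and the other's has not, the two risks are not measured on the same scale, even though they carry the same outcome name. Section 5.2 itself lists misreporting of outcomes as possible, so some removals should be expected.

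Three results are at stake:

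- the contextual (iv)(a) risk, which will be read beside the rivaroxaban primary result;
- the composite (iv)(b), where the plan does not say whether the rivaroxaban part uses adjudicated or reported cases;
- the odds ratio for anticoagulant in Section 4.7.6, if that model is run.

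The primary objective is a single-cohort estimate and does not depend on how contextual cases are handled.

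**Working it through.** **1. Where the rule is and is not stated**

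- Sections 4.7.2 and 4.7.5 both speak of reports and both take the first as the incident event. Only 4.7.2 adds expert adjudication, removal and restriction to confirmed cases.
- Section 4.4.2.5 and Table 4 provide follow-up of major bleeds without limiting it to one cohort. It is there to gather more information on matters such as severity, management and risk factors. No rule turns it into reclassification or removal.
- Section 4.8 assesses drug-relatedness, not whether a bleed meets Table 2.
- The sensitivity analysis in 4.7.5 that mentions confirmation on follow-up concerns primary-care events added to check under-reporting.
- The note to Table 2 has the steering committee confirm the case definition, not individual cases.

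The mismatch is confined to the primary-site bleeds. Other-site major bleeds and clinically relevant non-major bleeds fall under 4.7.5 in both cohorts.

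**2. The plan's own figures**

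Section 4.2.1 uses n = 3.84 × p(1 − p) / d².

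- DVT/PE: 3.84 × 0.004 × 0.996 / 0.0039² = 1005.8 (plan: 1005).
- AF: 3.84 × 0.007 × 0.993 / 0.0069² = 560.6 (plan: 561).

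Both reproduce, and this point disputes neither. They supply the expected risks used below.

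**3. Expected true cases per cohort**

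Pooled risk = (1005 × 0.004 + 561 × 0.007) / 1566 = 7.947 / 1566 = 0.507%. In 1700 patients that is 8.6 cases. Splitting 1700 exactly 2:1 gives 1133 × 0.004 + 567 × 0.007 = 8.5, practically the same. Applying the rivaroxaban risks to the contextual cohort is an assumption, made to represent equal true risk.

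**4. Effect of one-sided removal**

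Let c be the share of contextual reports that adjudication would confirm. The contextual count as reported is (true cases) / c, so

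apparent risk ratio = true risk ratio × c.

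The documents give no value for c; the range is assumed. With a true ratio of 1:

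| c (assumed) | Contextual risk as reported | Contextual reports per 1700 | Rivaroxaban confirmed per 1700 | Apparent ratio |
|---|---|---|---|---|
| 1.0 | 0.507% | 8.6 | 8.6 | 1.00 |
| 0.9 | 0.564% | 9.6 | 8.6 | 0.90 |
| 0.8 | 0.634% | 10.8 | 8.6 | 0.80 |
| 0.7 | 0.725% | 12.3 | 8.6 | 0.70 |
| 0.6 | 0.846% | 14.4 | 8.6 | 0.60 |
| 0.5 | 1.015% | 17.3 | 8.6 | 0.50 |

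Odds ratios are almost identical because the risks are small (0.899 at c = 0.9, 0.698 at 0.7, 0.497 at 0.5).

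**5. Against sampling error**

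The Poisson standard deviation at 8.6 cases is √8.6 ≈ 2.9. The exact 95% interval for 9 cases in 1700 is 0.24% to 1.00%. At c = 0.9 the distortion is about one case and is lost in the noise. Only at c = 0.5 does the contextual risk (1.015%) reach the upper limit of that interval. The direction, however, is fixed: since c cannot exceed 1, the asymmetry never works against rivaroxaban.

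**The case against.** The case on the other side has real force.

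- **Silence is not a statement.** Nowhere does the plan say that contextual bleeds will go unadjudicated. The phrase about numbers of reports opens a general paragraph on signal detection, and 4.7.2 uses the word reports for its own adjudicated numerator. A reader might infer that contextual bleeds will simply be counted as reported. The documents support only that no adjudication rule is stated for them. This stands, so the effect is conditional.
- **Other controls apply to both cohorts.** Table 2 criteria, Table 4 follow-up, data queries under Section 4.5.2 and the steering committee's case definition all reduce misclassification. They narrow the gap, but none is a removal rule. Operational detail might also sit in an analysis plan or data management plan that is not shown. Even so, the protocol states the rule for one cohort and not the other.
- **The plan disclaims the comparison.** This stands and limits the consequence. It does not remove it, because the same bleeds are quantified in both cohorts and 4.7.6 allows for an anticoagulant odds ratio. With about 8.6 cases per cohort that model may never be run.
- **Section 4.3.2 is not contradicted.** A reader might take its sentence on measurement error as a promise that cases are reviewed identically. It speaks of data collection under a common protocol, not of case review afterwards.
- **The composite may be consistent.** If 4.7.5 governs (iv)(b) for both cohorts, no asymmetry arises there. The fault is that the plan does not say.
- **The size is assumed.** The ratio equals c by construction, and c has no source in the documents.

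**Conclusion.** The plan specifies expert adjudication and removal of misreported primary-site bleeds for rivaroxaban only, and states no equivalent for the contextual cohort. Followed as written, the rivaroxaban primary result and the contextual (iv)(a) result use different case standards. The 4.7.6 model, if run, could mix the two, and the basis of the rivaroxaban part of composite (iv)(b) is left open.

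The effect would be to multiply rivaroxaban's apparent relative risk by c, somewhere between 0.5 and 1.0 on an assumed range. This rests on contextual bleeds in fact not being adjudicated and on adjudication identifying false reports correctly. The case counts also assume equal true risk at the plan's rivaroxaban rates.

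A reader might conclude that rivaroxaban will look safer than its context. The documents do not support that as a prediction: the contextual handling is unstated, c is unknown, and the expected counts are small. What they support is a gap affecting secondary and contextual results, not the primary estimate. It is worth closing because it is cheap to close.

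**What to change.** - In Sections 4.7.5 and 4.7.6, state that reported GI, urogenital and intracranial bleeds in both cohorts go through the same expert adjudication, case definition and removal rule as in 4.7.2.
- Base objectives (iv)(a) and (iv)(b) and the 4.7.6 model on adjudicated cases in both cohorts.
- Give as-reported counts for both cohorts as a sensitivity analysis. The examination of excluded incomplete cases already planned in 4.7.2 covers part of this for rivaroxaban.
- Optionally, mask the reviewers to drug and cohort where feasible. Masking will be imperfect, since INR values or reversal treatment can reveal the drug.

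The cost is a wording change and about 10 to 20 additional case reviews by the existing reviewers (9.6 to 17.3 expected contextual reports for c from 0.9 to 0.5). Table 4 already provides for follow-up information on major bleeds and is not limited to rivaroxaban. No sample-size figure changes.

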# Total number of new cases during 12 week observation period x 100 Population initially at risk

If the observed cumulative incidence from the SCEM study falls within the range expected as set by the precision limits of cumulative incidence from clinical trial data, then the null hypothesis (of no difference) will not be rejected. Cumulative hazard rate methods account for truncation of exposure time and censoring; for these analyses the exposure time would be censored at the time of the first event. Kaplan-Meier plots will be presented to describe timeto event as well as smoothed hazard plots to describe how the baseline risk of an event changes over time. Estimates of the hazard function will also be modelled to determine whether the baseline hazard (risk) of the event increases or decreases with time. A constant hazard over time may be consistent with a background (not caused by the drug) event rate, whereas a non-constant hazard over time may be an indicator of a drug-event relationship. The null hypothesis that the hazard rate of the selected event in patients prescribed rivaroxaban will be constant during the 12 week period following the start of treatment will be tested by fitting a parametric time to event model (e.g. Weibull). Such models have a shape parameter that indicates whether the hazard is significantly increasing or decreasing over time. At least five reports of an event are deemed necessary for modelling purposes.\*\*\*\*\*\*

Several sensitivity analyses will be performed: In one, observation start date will be imputed to be the same as the diagnosis date (i.e the index date will be shifted backwards in time) for those patients for whom a lag period between diagnosis and receiving rivaroxaban treatment was reported. The application of time-varying covariates methodology will enable examination of the impact of any transition from other treatments given as part of initial standard care on the results. In addition, since the primary analysis will be run only to include confirmed cases of incident major bleeding, it will be necessary to explore the reasons for exclusion of incomplete cases and examine their impact on the estimated measure of frequency.

Where possible, data will be stratified according to relevant strong risk factors (e.g. gender, age ( $\leq 60, 60-74, \geq 75$  years), indication and past history of haemorrhage or VTE) and stratum-specific incidence rates examined.

Graphs of cumulative counts of events of interest, by month over the study period, will be examined for possible change in reporting over calendar time.

4.7.3. To describe the health profile of patients at index date prescribed treatment with rivaroxaban in the secondary care hospital setting and the treatment programme they received to advance the understanding of the rivaroxaban patient population in actual clinical practice in relation to the contextual cohort.

\*\*\*\*\*\* e.g. when the shape parameter (p) for the Weibull model is equal to one, the hazard is estimated to be constant over time, if p is greater than one the hazard is increasing, if p is less than one the hazard is decreasing. The hazard function will be determined as non-constant if the 95% CI excludes the value one

The following relates to Section 2.2.2 secondary objective (ii). Valid cohort demography (patient self-reported: age, gender, ethnicity, socioeconomic index) will be presented separately for both rivaroxaban and the contextual cohort, as reported at index date using all available information from questionnaires (completed by patient and specialist HCP). Other patient self-reported general health factors [BMI, weight, height, smoking and alcohol use] and indication-related characteristics [primary (and secondary if provided) diagnosis/decision, date and duration since first ever recorded; stroke and reported bleeding risk factors; pattern of most recent INR/APTT levels if switching from prior anticoagulant]; anticoagulant treatment initiation programme by specialist HCP (index date, dose and frequency) and non-clinical prescribing reasons. A synopsis of pre-index and concurrent relevant morbidities and medication use will also be provided.

For rivaroxaban cohort only, patient subgroups of special interest (Table 5 – 'off-label' use defined as arising from contraindications and those for which: a) precautions for use are recommended; b) appropriate clinical monitoring is recommended; c) limited information is available; and d) selected concomitant drug use) will be summarised in order to inform on real-life use of rivaroxaban. The proportion of patients within each special population sub-group prescribed rivaroxaban who had *one or more* relevant characteristics/conditions/co-prescribed medications at index date will also be summarised within each indicator group by simple aggregation of counts (Table 5).

Further stratification within-cohort by calendar period *may* also be undertaken to identify any cohort effects or trends that may be emerging.

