From rivaroxaban clinical trial data, the cumulative incidence of each of the primary outcome major bleeding events (GI, urogenital and intracranial) in patients taking rivaroxaban for DVT and prevention of recurrent DVT and PE over 12 weeks of treatment was approximately 0.2%, 0.1% and 0.0%, respectively. Since information on the reported incidence for intracranial major bleeding outcomes within the first 12 weeks of treatment is limited, the reported incidence of intracranial haemorrhage with enoxaparin/vitamin K antagonist (VKA) from RCTs of 0.1% within 12 weeks will be used as an estimate of the incidence of that event in this population for rivaroxaban. From clinical trial data, the cumulative incidence of the primary outcome major bleeding events was similar in patients taking rivaroxaban for PE (~0.3%). As such, we do not expect any difference in cumulative incidence of bleeding between PE and DVT patients.

The formula used to calculate the sample size based on an estimation of the proportion of patients who will experience major bleeding outcomes is[33]:

Sample size= 
$$3.84 \times p(1-p)$$
 \_where p= estimated proportion (cumulative incidence)  
(precision)

Thus in this population of patients taking rivaroxaban for the treatment of DVT and PE and prevention of recurrent DVT and PE, in order to estimate the expected (true) cumulative incidence of the primary outcomes of major bleeding (GI, urogenital and intracranial) of 0.4% (0.2%, 0.1% and 0.1%, respectively), within  $\pm 0.39\%$ , we would need a sample size of 1005 patients (Epi Info v6).

The cumulative incidence of each of the primary outcome major bleeding events (GI, urogenital and intracranial) in patients taking rivaroxaban for the prevention of stroke and systemic embolism in adult patients with non-valvular atrial fibrillation over 12 weeks of treatment was approximately 0.5%, 0.1% and 0.1%,‡‡‡ respectively. [5] Thus, in this population of patients taking rivaroxaban for the prevention of stroke and systemic embolism in adult patients with non-valvular atrial fibrillation, in order to estimate the expected (true) cumulative incidence of the primary outcomes of major bleeding (GI, urogenital and

<sup>‡‡‡ Approximate estimates of cumulative incidence in 12 weeks of treatment, based on steady increase in incidence over time and overall cumulative incidence from a median of 590 days treatment exposure (90/590\*N)

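### Section 4.7.2 divides on-treatment bleeds by all starters, so as a 12-week risk the primary figure reads low when patients stop early or are lost, and the trial-comparison rule becomes less likely to flag an excess.

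*Supplement*

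**What the plan says.** Protocol section 4.7.2 covers the primary objective, haemorrhage on rivaroxaban.

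- **At-risk time.** "For purposes of this analysis the denominator (personperiod at risk) is defined as the 12 week observation period", which runs from the first prescription "until the date of stopping (+ 2 days) or at 12 weeks if patient did not stop, whichever occurs first".
- **Events.** The numerator is "reports of incident major bleeding events during that 12 week observation period", so it covers the same truncated window.
- **Formula.** Cumulative incidence is then "Total number of new cases during 12 week observation period" over "Population initially at risk", times 100.
- **Decision rule.** If the observed cumulative incidence lies within the precision limits set around the trial figure, the null hypothesis of no difference is not rejected.
- **Other estimates.** Cumulative hazard rates with 95% CI and Kaplan-Meier plots are also planned. The section itself says: "Cumulative hazard rate methods account for truncation of exposure time and censoring". It does not say which estimate leads, or which enters the rule if they differ.

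Section 4.2.1 gives the reference values as approximate cumulative incidences over 12 weeks of treatment: 0.4% for DVT/PE and 0.7% for AF. A footnote says the AF figures were scaled by 90/590 from a median exposure of 590 days.

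**The concern.** Under the formula a patient who stops at week 3 cannot contribute a bleed after stop + 2 days, yet counts in the denominator as if observed for all 12 weeks. The executive summary describes the target as haemorrhage in the 12 weeks after treatment initiation; section 4.7.2 speaks of outcomes during treatment. The formula fits only the second, and only with complete follow-up.

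Follow-up need not be complete. Section 4.1 lets observation end early when specialist care ends. Section 4.3.2.3 removes a patient from the primary analysis only if both the specialist and the GP 12-week forms are blank or unreturned. A patient discharged at week 3 whose GP does not reply therefore stays in the denominator with about three weeks observed, and section 4.4.3.1 expects some non-response. That is censoring whatever the target, and a crude proportion cannot handle it.

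At stake is the one formal comparison in the primary analysis. A figure that reads low moves it towards a finding of no difference, in a study with a stated particular focus on patients who stop or switch early.

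**Working it through.** **Inputs from section 4.2.1.** DVT/PE 0.4% ± 0.39%, N = 1005; AF 0.7% ± 0.69%, N = 561.

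**Step 1: the plan's own sample sizes.** n = 3.84·p(1−p)/precision².
- DVT/PE: 3.84 × 0.004 × 0.996 / 0.0039² = 1005.8 (stated 1005).
- AF: 3.84 × 0.007 × 0.993 / 0.0069² = 560.6 (stated 561).

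Both reproduce.

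**Step 2: the crude proportion relative to the on-treatment 12-week risk.** The documents give no stopping rate, so s = 10-40% stopped by day 84 is an assumption. Assume also exponential stopping unrelated to bleeding, a constant bleeding hazard and rare events. With λ = −ln(1−s)/84 and the two-day lag,

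ratio = [2 + (1 − e^(−82λ))/λ] / 84.

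At s = 20%: λ = 0.002657, so (1 − 0.8043)/0.002657 ≈ 73.7 and the ratio is 75.7/84 = 0.901.

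| Stopped by week 12 | Ratio | Loss on 0.4% (points) | Loss on 0.7% (points) |
|---|---|---|---|
| 10% | 0.951 | 0.02 | 0.03 |
| 20% | 0.901 | 0.04 | 0.07 |
| 30% | 0.848 | 0.06 | 0.11 |
| 40% | 0.792 | 0.08 | 0.15 |

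**Step 3: other assumptions over the same 10-40%.**
- Stopping uniform over 12 weeks, constant hazard: relative shortfall 4.8-19.0%.
- Stopping uniform, front-loaded hazard (Weibull shape 0.5): 3.1-12.5%.
- All stopping at week 3, constant hazard: 7.3-29.0%.

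A simulation of 4 million patients with 30% stopping uniformly and a true risk of 0.400% gave 0.345% for the crude proportion and 0.402% for Kaplan-Meier.

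**Step 4: effect on the rule.** The ranges are 0.01-0.79% (DVT/PE) and 0.01-1.39% (AF). The lower limits correspond to 0.10 and 0.06 cases, so on the low side only a count of zero falls outside. The upper limits are 1005 × 0.0079 = 7.94 and 561 × 0.0139 = 7.80 cases, so an excess is flagged at 8 or more cases in either group. Binomial probability of at least 8 cases when the true risk is 2.5 times the reference:

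| | No stopping | 20% stop | 30% stop |
|---|---|---|---|
| DVT/PE, true risk 1.0% | 0.786 | 0.684 | 0.618 |
| AF, true risk 1.75% | 0.765 | 0.659 | 0.593 |

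Put another way, at 20% stopping the true risk that would on average sit at the upper limit rises from 0.79% to 0.79/0.901 = 0.88% for DVT/PE, and from 1.39% to 1.39/0.901 = 1.54% for AF.

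**The case against.** The strongest reply is that section 4.7.2 names its target as outcomes during treatment. If stopping is a competing event and every patient is fully observed, cases over starters is a standard, unbiased estimate of that probability. This stands. A reader might infer that the figure is too low whenever anyone stops, or that it estimates nothing meaningful; the documents support neither. Stopping because of a counted bleed causes no understatement at all.

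A reader might also infer that the plan overlooks censoring. It does not: cumulative hazards with 95% CI and Kaplan-Meier plots are in the same section. Section 4.7.5 adds on-treatment incidence densities, rates for the first week after stopping and, where time-to-event models are fitted, a sensitivity analysis extending to seven days after stopping. The person-period wording may have been meant for the hazard estimate. No separate SAP is shown, and some detail could sit there. What remains is that the only formula given for cumulative incidence, and the only estimate the rule names, is the one that ignores censoring.

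The effect is modest in absolute terms. About four events are expected per indication (1005 × 0.4% = 4.0; 561 × 0.7% = 3.9), so 20% stopping removes about 0.4 expected events against a Poisson SD of about 2.

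Two further inferences should not be drawn. The documents do not show how the DVT/PE trial figure handled discontinuation, so it cannot be called a full-exposure figure; if it is a crude proportion, the comparison is closer to like with like. And scaling the AF reference to 90 days rather than 84 has no practical effect: 0.5/0.1/0.1% times 84/90 is 0.47/0.09/0.09%, which rounds back to the same figures.

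**Conclusion.** The concern holds in a limited form. The at-risk definition and the formula in section 4.7.2 do not match, the estimand is not stated, and the formula feeds the comparison with trial incidence over 12 weeks of treatment. For the risk under continued treatment, or for all bleeds within 12 weeks of starting, the primary figure is biased low under early stopping or loss of observation.

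The 5-21% relative shortfall rests on an assumed 10-40% stopping by week 12, stopping unrelated to bleeding, and a constant hazard; the other patterns in the working run from 3% to 29%. The main-case loss of 0.02-0.15 points is inside the planned ±0.39 and ±0.69 points, so it does not overturn the sample size. It does weaken the rule's ability to flag an excess: at 20% stopping and a true risk 2.5 times the reference, by about 10 percentage points in either indication. The textual mismatch is certain; the size of the bias depends on a stopping rate the documents do not give. The point is worth correcting before analysis, but it does not invalidate the study.

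**What to change.** In section 4.7.2:

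1. State the estimand: risk of a primary bleed by day 84 while on treatment as if treatment continued, risk of an on-treatment bleed among starters, or risk of any such bleed within 12 weeks of starting.
2. For the comparison with trial incidence over 12 weeks of treatment, make the day-84 Kaplan-Meier risk (or Aalen-Johansen with death as a competing event), censored at stop + 2 days or end of observation, with 95% CI and by indication, the primary estimate and the input to the rule.
3. Keep cases over starters as a descriptive line.
4. Add a supportive as-started day-84 estimate that counts all bleeds to week 12 whatever the treatment status.
5. Reconcile the person-period wording with the formula, for example by tying it to the hazard estimate only.
6. Optionally, scale the AF reference to 84 days for consistency.

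The cost is wording: stop dates are already collected on the 12-week questionnaire and survival methods are already planned. The interval will be slightly wider than the crude binomial one. Censoring at stopping assumes that stopping is non-informative, which is doubtful if patients stop for minor bleeding or poor tolerance. That assumption should be stated; the as-started estimate shows how much depends on it.
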